6.4.8.3.4. Incidence of Post-baseline New-Onset of Diabetes

The number of subjects who shift from no diabetes at baseline (defined as no medical history of diabetes in the targeted medical history CRF, HbA1c $< 6.5\%$ at baseline, and fasting glucose < 126 mg/dL at baseline (note that baseline is defined as the average of Screening and Day 1 fasting glucose values, if one fasting glucose value is missing (Screening or Day 1), the assessment will be based on the available data) to diabetes will be summarized. A 4-component definition of diabetes will be utilized. The 4 components are provided below.

1. Diabetic TEAEs identified by the SMQ search (see [Appendix 5](#)), or
2. Post-baseline fasting glucose ≥ 126 mg/dL on two consecutive occasions, or
3. Initiation of anti-diabetic medication at any time post-baseline, or
4. At least one post-baseline Hba1c $\geq 6.5\%$.

The number of subjects who have any of the 4 components will be summarized (post-baseline new-onset of diabetes) along with each component. This analysis will be performed for those subjects who have fasting glucose at baseline < 100 mg/dL and then for those with fasting glucose at baseline ≥ 100 and < 126 mg/dl (normoglycemic).

The time to new-onset diabetes will also be summarized. Only subjects without diabetes at baseline will be included in the analysis. The time (weeks) to new-onset diabetes will be calculated from the date of the first administration of study drug.

6.4.8.4. Anti-Drug Antibody

ADA is being assessed and will be listed in a separate ADA report. If there are ADA findings, further characterization and additional evaluations may be performed on safety and efficacy parameters.

6.4.8.5. Vital Signs

Observed value, change, and percent change from Day 1 in vital signs will be summarized descriptively at each scheduled time point by treatment group.

The change from baseline to EOS will also be summarized by the following categories:

- Systolic blood pressure (mmHg):
 - ≤ -20
 - > -20 to ≤ -10
 - > -10 to ≤ -5
 - > -5 to < 5
 - ≥ 5 to < 10
 - ≥ 10 to < 20
 - ≥ 20
- Diastolic blood pressure (mmHg):
 - ≤ -10
 - > -10 to ≤ -5
 - > -5 to ≤ -3
 - > -3 to < 3
 - ≥ 3 to < 5
 - ≥ 5 to < 10
 - ≥ 10

6.4.8.6. Electrocardiograms

The percentage of subjects with abnormal ECG findings reported as AEs will be summarized by treatment group within the overall assessment of cardiac safety.

6.4.8.7. Neurological Examinations

The percentage of subjects with a treatment-emergent abnormal neurological event and the specific abnormality reported as adverse events, will be summarized by treatment group.

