#### 10.3.3. Analysis Windows and Baseline

The observational period for the study includes the screening period (Day -14 to Day -1), the treatment period (Day 1 to Day 510), and the EOS visit (Day 540). Any event occurring beyond the defined observational period, even if collected on the eCRF, will not be included in the planned statistical analysis. However, all data, including that reported after the defined observational period, will be included in the subject data listings.

Analysis windows will be defined to maximize the amount of data that are included in the analysis models. Full details will be provided in the SAP.

Unless otherwise specified, for evaluations that are collected at multiple occasions prior to initiation of investigational product administration, the latest evaluation will be considered the "Baseline" evaluation for analysis.

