#### 10.4.4.4. Neurological Examinations

The percentage of subjects with a treatment-emergent abnormal neurological examination and the specific abnormality reported will be summarized by treatment group.

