2.4. Schedule and Sequence of Procedures

The Schedule of Assessments (Table 1) summarizes the study assessments by time point.

This study consists of four periods: Screening, Randomization, Treatment, and End of Study.

- **Screening period (Days -14 to -1):** occurs prior to randomization and consists of confirming eligibility and collecting baseline assessments.
- **Randomization (Day 1):** occurs on the day of initial administration of investigational product.
- **Treatment period (Day 1 through Day 510):** occurs from the start of investigational product administration through the final clinic visit.
 - Dosing: Day 1, Day 90, Day 270, and Day 450 (final dose)
 - Additional clinic visits: Day 30, Day 150, Day 330, and Day 510
- **End of study (EOS) visit:** Day 540 (90 days past last dose)

For subjects who decided to prematurely and permanently discontinue from study treatment and who decline further follow-up visits, EOS visit will be scheduled as soon as possible. If decision to discontinue is made at a specific visit, this visit will become the EOS visit and EOS visit procedures should be followed.

The expected duration of the subjects' involvement in the study will be approximately 554 days which includes screening, investigational product administration, and the EOS period to Day 540.

Schedule of Assessments

Table 1: Study Design and Schedule of Assessments

Visits	Screening	Randomization	Treatment							EOS ¹
		V1 (baseline)	V2	V3	V4	V5	V6	V7	V8	V9 (90 days post last dose)
Timelines	Day -14 to -1	Day 1	Day 30	Day 90	Day 150	Day 270	Day 330	Day 450	Day 510	Day 540
Visit windows (± days)			±2	±30	±30	±30	±30	±30	±14	±14
Informed consent	X									
Assessment of eligibility	X	X ²								
Demographics and medical history	X									
Pregnancy test	X ³	X ³		X ³		X ³		X ³	X ³	X ³
Randomization		X								
Investigational product administration		X ^{4,5}		X ^{4,5}		X ^{4,5}		X ^{4,5}		
Physical examination	X									X
Neurological examination		X								X
Weight/height/waist circumference	X ⁶									X
Vital signs ⁷	X	X		X		X		X		X
12-lead ECG	X	X								X
Fasted lipid profile/biomarkers ⁸	X	X		X	X	X	X	X	X	X
ADA		X ⁹	X ⁹	X ⁹	X ⁹	X ⁹	X ⁹	X ⁹	X ⁹	X ⁹
Full Serum chemistry ¹⁰		X								X
Limited serum chemistry ¹⁰	X			X	X	X	X	X	X	
Urinalysis (local) ¹¹	X	X								X
Hematology and coagulation ¹²	X	X			X					X
Previous/concomitant medications	X	X	X	X	X	X	X	X	X	X
AEs/SAE reporting	X	X	X	X	X	X	X	X	X	X

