3.5. Additional NON DOSING Clinic Visits (Days 150, 330, and 510)

Subjects will return to the clinic for dosing follow-up visits 60 days following each dose of investigational product. The following assessments will be completed during these visits:

3.5.1. Day 150

- Fasting lipid profile/biomarkers ([Section 3.9](#))
- Assessment of ADA ([Section 3.8.8.7](#))
- Central clinical laboratory (limited serum chemistry and hematology and coagulation) ([Section 3.8.8](#))

- Concomitant medications
- AE/SAE reporting

3.5.2. Day 330

- Fasting lipid profile/biomarkers ([Section 3.9](#))
- Assessment of ADA ([Section 3.8.8.7](#))
- Central clinical laboratory (limited serum chemistry) ([Section 3.8.8](#))
- Concomitant medications
- AE/SAE reporting

3.5.3. Day 510

- Pregnancy test (performed locally, using central laboratory supplies, if applicable) (women of childbearing potential only)
- Fasting lipid profile/biomarkers ([Section 3.9](#))
- Assessment of ADA ([Section 3.8.8.7](#))
- Central clinical laboratory (limited serum chemistry) ([Section 3.8.8](#))
- Concomitant medications
- AE/SAE reporting

3.6. End of Study (EOS) Visit (Day 540 – 90 days post last dose)

A subject's participation in the study is complete when the final visit, 90 days after the last dose of investigational product, has occurred. The following assessments will be completed during this visit:

- Pregnancy test (performed locally, using central laboratory supplies, if applicable) (women of childbearing potential only)
- Physical examination (including weight and waist circumference)
- Neurological examination (Protocol Appendix C)
- Vital signs: blood pressure and heart rate ([Section 3.8.3](#))
- 12-lead ECG
- Fasting lipid profile/biomarkers ([Section 3.9](#))
- Collection and storage of serum samples for possible future use to detect the formation of ADA ([Section 3.8.8.7](#))
- Central clinical laboratory (full serum chemistry, hematology and coagulation) ([Section 3.8.8](#))
- Urinalysis (performed locally, using central laboratory supplies)

- Concomitant medication
- AE/SAE reporting
- All ongoing SAEs have been followed to resolution

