3.8.5. Neurological Evaluation

A full neurological examination will be performed as per the Schedule of Assessment (Protocol Appendix C).

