6.4.8.1. Adverse Events

The Medical Dictionary for Regulatory Activities (MedDRA) dictionary (v20.1) will be used for coding AEs. An AE (classified as preferred term) occurring during the treatment period will be counted as a treatment emergent AE (TEAE) either if it is not present at Day 1 before treatment or if it is present before treatment but increased in severity during the treatment period.

The following summary tables will be presented:

- Overall Summary of TEAEs
- TEAEs by SOC and PT
- TEAEs by PT
- Common (2% within either treatment group) by PT
- TEAEs by SOC, PT, and Severity

- TEAEs by SOC, PT, and Relationship to Study Drug
- Related TEAEs by SOC, PT, and Severity
- Treatment Emergent Serious AEs (TESAEs) by SOC and PT
- TESAEs by PT
- TESAEs by SOC, PT, and Severity
- TESAEs by SOC, PT, and Relationship to Study Drug
- Related TESAEs by SOC, PT, and Severity
- TEAEs Leading to Withdrawal of Study Treatment by SOC and PT
- TEAEs with a Fatal Outcome by SOC and PT

If more than one event occurred with the same preferred term for the same subject, the subject will be counted only once for that preferred term using the most severe or related occurrence for the summary by severity, or relationship to study drug, respectively.

For common (2% within either treatment group) TEAEs, serious TEAEs and TEAEs leading to withdrawal of study medication, risk ratios along with 95% confidence intervals will be presented to compare treatment groups with respect to risk.

The following additional adverse events (Refer to [Appendix 5](#), Additional Adverse Events Investigations) will also be assessed:

1. Adverse Events at the Injection Site
2. Hepatic events
3. Renal events
4. Hypersensitivity
5. Neurological events and Neurocognitive disorders
6. Ophthalmological events

Clinically relevant TEAEs at the injection site will also be tabulated. See [Appendix 6](#) for a list of clinically relevant injection site preferred terms.

The time to the first TEAE at the injection site will also be summarized. Only subjects with a TEAE at the injection site will be included in the analysis. The time (hours) will be calculated from the date of the most recent administration of study drug. The duration of the TEAE will also be summarized. The same analyses will be performed for each individual TEAE PT at the injection site. The time to the first clinically relevant adverse event at the injection site will be analyzed similarly.

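### Read literally, the treatment-emergent period ends at Day 510, so deficits dated to the only post-baseline neurological examination (EOS, Day 540) fall outside the planned summary

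*SAP*

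**What the plan says.** **Examination timing.** SAP 3.8.5 states: "A full neurological examination will be performed as per the Schedule of Assessment (Protocol Appendix C"). In the schedules (Protocol Table 2, SAP Table 1) the neurological row is marked at V1 (Day 1) and V9 (EOS) only. The visit lists agree: the item "Neurological examination (Protocol Appendix C") appears under randomization (SAP 3.2) and under the EOS visit (SAP 3.6), and at no other visit.

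**Treatment period.** SAP 2.4 gives "Treatment period (Day 1 through Day 510") and lists the Day 540 EOS visit as a separate period. Protocol 10.3.3 makes the same split within the observational period: "the treatment period (Day 1 to Day 510), and the EOS visit (Day 540"). SAP 2.4 also describes the treatment period as one that "occurs from the start of investigational product administration through the final clinic visit".

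**Treatment-emergent rule.** SAP 6.4.8.1: "An AE (classified as preferred term) occurring during the treatment period will be counted as a treatment emergent AE (TEAE"), provided the event was absent before treatment or has worsened since. Protocol 10.4.4.1 has the same rule. Neither adds a follow-up extension.

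**Neurological summary.** Protocol 10.4.4.4 plans "The percentage of subjects with a treatment-emergent abnormal neurological examination" by arm. SAP 6.4.8.7 plans "The percentage of subjects with a treatment-emergent abnormal neurological event and the specific abnormality reported as adverse events". Protocol 8.3.2 and SAP 4.5.2 require an abnormal neurological examination to be reported as an AE.

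**Dates.** SAP 6.3.4.2 treats AEs with missing dates as treatment emergent. It does the same for incompletely dated AEs unless the onset is specific enough to show that they began before the first dose.

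**The concern.** A scheduled, blinded examination at baseline and at the end of follow-up is meant to detect deficits that patients do not report. Its value lies in comparing the two time points by arm. Here the second time point lies after the period that decides whether an event is treatment emergent, and the planned output admits only treatment-emergent events. A sign first elicited at EOS and dated to that visit is an AE, but not a TEAE.

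The planned neurological summary could therefore under-count because of a definition. Two programmers could also build different tables from the same data, one applying the Day 510 limit and the other counting everything up to EOS.

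**Working it through.** No sample-size figure bears on this point. The check is a timeline, set against the definitions.

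**1. The plan's own dates (SAP 2.4 and Table 1).**
- EOS is 90 days after the last dose: 450 + 90 = 540, as stated.
- Duration with 14 days of screening: 14 + 540 = 554 days, as stated.

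**2. Where the EOS examination falls.** The windows at Day 510 and Day 540 are both ±14 days.

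| Quantity | Arithmetic | Result |
|---|---|---|
| Earliest in-window EOS examination | 540 − 14 | Day 526 |
| Latest in-window EOS examination | 540 + 14 | Day 554 |
| Gap from Day 510, shortest | 526 − 510 | 16 days |
| Gap from Day 510, nominal | 540 − 510 | 30 days |
| Gap from Day 510, longest | 554 − 510 | 44 days |
| Latest in-window Day 510 visit | 510 + 14 | Day 524 |
| Gap from that visit to the earliest EOS | 526 − 524 | 2 days |

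Even if the period ended at each subject's actual Day 510 visit, an in-window EOS examination would still come at least 2 days later.

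**3. Scheduled post-baseline neurological examinations inside the treatment-emergent period, for a completer.**
- Period taken as Day 1 to Day 510: 0.
- Period taken as first dose through EOS: 1.

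**4. Fate of a new deficit found at a completer's EOS examination.**

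| Onset as recorded | Treatment emergent as written? |
|---|---|
| Complete date on or before Day 510, after first dose | Yes |
| Missing start date | Yes (SAP 6.3.4.2) |
| Incomplete date, not shown to precede first dose | Yes (SAP 6.3.4.2) |
| Complete date after Day 510, including the examination date | No |

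The same clinical finding moves in or out of the summary according to its recorded date. A subject who stops early and declines further visits has the EOS procedures brought forward (SAP 2.4). If that examination falls on or before Day 510, a finding dated to it counts; the same finding at a completer's EOS does not.

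**5. Other EOS assessments.** After Day 1, the scheduled physical examination, ECG and urinalysis are also done only at EOS (SAP Table 1). Significant changes or abnormal results become AEs (SAP 3.8.4, 3.8.6, 3.8.8.5), so those dated to EOS meet the same limit in the TEAE tables. The dedicated ECG summary in SAP 6.4.8.6 does not: it takes abnormal ECG findings reported as AEs, with no treatment-emergent restriction.

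**The case against.** The strongest reply is that the authors plainly meant EOS to count, and that the Day 510 limit is one reading of loose text. There is good support for this:

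- SAP 2.4 says the treatment period "occurs from the start of investigational product administration through the final clinic visit", while SAP 3.6 and Protocol 6.8 treat Day 540 as the final visit.
- The TEAE definitions cite no day number.
- The incomplete-date rule in SAP 6.3.4.2 tests only for onset before the first dose and sets no upper limit.
- Protocol 10.3.3 excludes from analysis only events beyond the observational period, and that period includes EOS.
- AEs are collected through EOS (Protocol 8.4.2).
- Protocol 10.4.4.4 plans a summary of treatment-emergent abnormal examinations, which for completers can come only from EOS.

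All of this stands as evidence of intent. It does not settle the rule, because the final-visit wording is attached to Day 510 and EOS is listed as its own period in the same list. That the written definition defeats the plan's own output is the reason to reconcile the two.

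A second reply is that neurological safety is covered elsewhere. AEs are recorded at every visit, SAP Appendix 5 has searches for demyelination, peripheral neuropathy and neurocognitive disorders, and the listings hold all data. This also stands in part: symptomatic events up to Day 510 will appear, and nothing is lost from the database. But the tables named in SAP 6.4.8.1 are TEAE or treatment-emergent SAE tables. The Appendix 5 searches do not say whether they are so limited, and they do not replace a summary of motor, gait and reflex findings by arm.

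A reader might go further and infer that no deficit found at EOS can enter the summary, or that it will be empty of examination findings for completers. SAP 6.3.4.2 and the onset-based definition do not support that, as the table of onset dates shows. Nor do the documents support a count of affected subjects. The 1425 in the sample-size section means evaluable for efficacy, not attending Day 540, and subjects who permanently stop study drug are asked to complete the remaining visits (Protocol 4.5.1).

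**Conclusion.** The point holds in a limited form. As written, AEs with a complete onset date after Day 510, including deficits dated to the EOS examination, are outside the SAP 6.4.8.7 summary and the TEAE tables. For in-window completers the examination always falls 16 to 44 days past the stated end of the treatment period. Deficits with earlier onset, or with missing or incomplete dates, are counted.

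This rests on reading the treatment period in SAP 6.4.8.1 as the one defined in SAP 2.4 and Protocol 10.3.3. If the final-visit wording were held to include EOS, the gap would close, but the documents do not say so.

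The number of findings affected cannot be estimated from the documents. The rule is the same in both arms, and no bias for or against inclisiran is shown. The efficacy analyses are not touched. It should still be corrected, because the literal rule can drop new findings from the only scheduled post-baseline neurological examination.

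**What to change.** In SAP 6.4.8.1, and in Protocol 10.4.4.1 to match, state that the treatment-emergent period runs from the first dose through the EOS visit, so that findings at EOS that were absent before the first dose, or have worsened since, count as treatment emergent. Say that this applies to SAP 6.4.8.7 and to all TEAE tables. That also covers AEs raised from the EOS physical examination, urinalysis and ECG.

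Optionally, if the eCRF holds a normal/abnormal result for the neurological examination, add a Day 1 to EOS shift by arm. That output would not depend on AE dating at all.

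The cost is one sentence in each document, plus one table if the option is taken. No new data are needed. The downside is slightly higher TEAE counts in both arms, because AEs dated between Day 511 and EOS would now be included.

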7. COMPUTER METHODS

Statistical analyses will be performed using SAS (version 9.4 or later version).

8. CHANGES TO ANALYSES SPECIFIED IN THE PROTOCOL

The following items were changed between the final version of the protocol and the final SAP.

- Primary efficacy endpoint analyses were modified per FDA feedback.
- Imputation methods were modified per FDA feedback.
- Subgroup analyses were added for select variables.
- A secondary efficacy endpoint was renamed from mean maximum percent change to maximum percent change.
- The exploratory endpoint, proportion of subjects in each group with any LDL-C reduction from baseline at any visit (responders), was added
- Identification of PCS/CS laboratory values were modified.

APPENDIX 1. DETAILS OF MMRM USED FOR EFFICACY ANALYSES

A number of efficacy analyses will utilize a mixed-effects model for repeated measures (MMRM). This includes the co-primary efficacy endpoints (in the case of the first co-primary efficacy endpoint, it will be used as a sensitivity analysis), the key secondary efficacy endpoints, and other secondary efficacy endpoints.

The models will generally include fixed effects for treatment, visit, baseline value, interaction between treatment and visit, and current use of statins or other lipid-modifying therapies. The visits will include Days 90, 150, 270, 330, 450, and 510, with Day 510 as the primary time-point. Linear combinations of the estimated means will be created for the various hypothesis tests.

The Restricted Maximum Likelihood (REML) estimation approach will be used with the covariance structure set as “Unstructured.” The least squares means will be calculated for each treatment at each visit.

The analysis will be carried out using the SAS PROC MIXED procedure.

Sample SAS statements follow:

```
ods output LSmeans=estimates;
ods output Diffs=lsdiffs;
Proc Mixed Data=ldl_data;
  Class treatment visit_day subject_id statiny;
  Model percent_change = treatment|visit_day statiny
base_value/DDFM=KR;
repeated visit_day/type=UN subject=subject_id;
LSMeans treatment*visit_day/cl pdiff=control('0' '510');
run;
```

(where ('0' '510') is the value of the placebo ['0'] at day 510 ['510'] in interaction term treatment*visit_day)

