#### 3. STUDY DESIGN

# 3.1. Type/Design of Study

[figure not shown]
This study will be a Phase III, placebo-controlled, double-blind, randomized trial in 1500 subjects with ASCVD (CHD, CVD or PAD) or ASCVD-risk equivalents (eg, type 2 diabetes and familial hypercholesterolemia, 20% or greater risk of a CV event as assessed by Framingham risk score or equivalent) and elevated LDL-C despite maximum tolerated dose of LDL-C lowering therapies to evaluate the efficacy, safety, and tolerability of inclisiran injection(s). The study will be a multicenter, international study (non-United States [US]). Informed consent will be obtained from subjects before the initiation of any study-specific procedures.

Subjects will be screened and approximately 1500 eligible subjects will be randomized: 750 subjects will be randomized to inclisiran sodium 300 mg and 750 subjects to placebo. Treatment allocation will be stratified by country and by current use of statins or other lipid-modifying therapies. Enrollment of statin intolerant subjects will be capped at 15% of total study enrollment. Each subject will receive an injection on Day 1 of blinded inclisiran or placebo, a second injection on Day 90 and subsequent injections on Day 270 and Day 450.

Subjects who have completed the study to Day 540 will be given the opportunity to enroll in a separate long-term extension study to collect long-term efficacy and safety data.

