The primary endpoints will use a reflexive LDL-C approach: either calculated LDL-C (based on the Friedewald formula) will be used, or if the calculated LDL-C is less than 40 mg/dL or triglycerides are greater than 400 mg/dL, or calculated LDL-C is missing, directly measured (using ultracentrifugation) LDL-C will be used if it is available.

Percentage change in LDL-C from baseline to Day 510

Missing values will be imputed for LDL-C after a reflexive approach using the multiple imputation (100 total imputed datasets) washout model specified in [Appendix 2](#). The percentage change in LDL-C at each visit will be calculated after the missing data imputation has been performed.

The primary analysis will be conducted on the ITT population and based on an ANCOVA model on the percentage change in LDL-C from baseline to Day 510 on each multiply imputed dataset (100 total). The model will include fixed effects of treatment group and current use of statins or other lipid-modifying therapies at baseline (yes or no) and baseline LDL-C as a covariate.

Treatment effects from these 100 ANCOVA analyses will then be combined using Rubin's Method via the SAS PROC MIANALYZE procedure. The difference in the least squares means

between treatment groups and corresponding two-sided 95% confidence interval will be provided for hypothesis testing.

See [Appendix 2](#) for more details on this analysis.

Time adjusted percentage change in LDL-C from baseline after Day 90 and up to Day 540.

A control-based pattern-mixture model (PMM), following the methods described in [Ratitch and O’Kelly \(2011\)](#), will be utilized to explore the possibility of data missing not at random (MNAR) for subjects who discontinued the study. For subjects who discontinued the study without any further follow-up data, their missing values after study discontinuation will be imputed under the assumption that their outcome would be similar to those in the placebo group with similar background characteristics. For subjects who did not discontinue the study, their intermittent missing values will be imputed based on the MAR assumption. Multiple imputations will be used to account for uncertainty in the imputation process and results from the imputed datasets will be combined using Rubin’s method [[Rubin, 1987](#)]. See [Appendix 3](#) for more details on this analysis.

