- Proportion of subjects in each group who attain global lipid targets for their level of ASCVD risk.

The two-sided 95% confidence interval for least squares means will be provided for continuous variables at a single point using an analysis of covariance model or using MMRM methods for variables measured over time (see [Appendix 1](#) for more details). The odds ratio and 95% confidence interval for the odds ratio will be provided for binary variables using logistic regression models. Nominal p-values will be provided when applicable.

Descriptive and graphical summaries by treatment group will also be presented.

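### As sketched in SAP Appendix 1, the MMRM code puts each arm's LS mean at a 50:50 mix of lipid-therapy users and non-users, although non-users are at most about 15%; a minor reporting correction

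*SAP*

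**What the plan says.** SAP Appendix 1 describes the MMRM used for the second co-primary endpoint, the key secondary endpoints, several other secondary endpoints and a sensitivity analysis of the first co-primary. It promises arm-level output: "The least squares means will be calculated for each treatment at each visit". The code is introduced with "Sample SAS statements follow". Three of its lines matter here:

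- "Class treatment visit_day subject_id statiny" makes `statiny`, the lipid-therapy factor, a classification variable.
- "Model percent_change = treatment|visit_day statiny" enters it as a main effect, with no interaction with treatment or visit.
- "LSMeans treatment*visit_day/cl pdiff=control('0' '510" begins the LS-means request, whose only options are `cl` and `pdiff`. No weighting option appears here or elsewhere in the SAP.

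SAP 6.4.6.1 shows that the factor has two levels, in the ANCOVA for the first co-primary endpoint: "current use of statins or other lipid-modifying therapies at baseline (yes or no) and baseline LDL-C as a covariate". SAP 6.4.6.2 commits to arm-level intervals: "The two-sided 95% confidence interval for least squares means will be provided for continuous variables".

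Protocol 3.1 limits the smaller level: "Enrollment of statin intolerant subjects will be capped at 15% of total study enrollment". Under Protocol 4.2, criterion 7, a subject not on a statin must be documented as intolerant. Protocol Appendix B, exception 4, admits such subjects on non-statin therapy, and these count as users of lipid-modifying therapy.

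**The concern.** An LS mean has to be evaluated at some mix of the classification factors. With no weighting option, PROC MIXED gives each level equal weight. The SAP's efficacy population is all randomized subjects, of whom at least about 85% take a statin or another lipid-modifying drug. An arm mean at a half-untreated mix describes a different population, and its standard error is driven by the small non-user group.

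What is at stake is the arm-level LS means and their 95% intervals by visit. The SAP also plans an arithmetic-mean version of the second co-primary endpoint (SAP 6.4.6.1.1), whose arm means sit at the enrolled mix. The two analyses could show different arm means for one endpoint for this reason alone.

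**Working it through.** **The plan's own figure.** SAP 6.1 gives a difference of 30 mg/dL, SD 20 mg/dL, 1500 randomized, 5% dropout and one-sided alpha 0.025. Then 1500 x 0.95 = 1425. The number per arm for 90% power is 2 x (20/30)^2 x (1.96 + 1.28)^2 = 9.3, so 10. With about 712 per arm, power is essentially 100%, so the stated figure of more than 90% is met. The weighting question does not touch it.

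**Inputs.** From the documents: n = 750 per arm, N = 1500, six visits in Appendix 1, and a non-user share p of at most about 0.15. Assumed: p between 0.05 and 0.15, a common correlation rho between visits of 0.3 to 0.7, and arms balanced on the factor. Equal weighting is the software default, not something the SAP states.

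**Formula.** At non-user weight w, the SE of an arm mean at one visit is

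SD x sqrt[1/n + (w - p)^2 x f / (N p (1 - p))].

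Here f = 1 for a single-visit ANCOVA. In the MMRM one coefficient is shared over six visits, so f = (1 + 5 rho)/6, which is 0.417 at rho = 0.3 and 0.75 at rho = 0.7. Observed margins set w = p and the second term vanishes. Equal weights set w = 0.5, so the SE ratio is

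sqrt[1 + 0.5 x (0.5 - p)^2 x f / (p (1 - p))].

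At p = 0.15 the term before f is 0.5 x 0.1225/0.1275 = 0.480. The ratio is then sqrt(1 + 0.480 x 0.417) = 1.10 at rho = 0.3, sqrt(1 + 0.480 x 0.75) = 1.17 at rho = 0.7, and sqrt(1.480) = 1.22 for one visit.

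| Non-user share | Term before f | MMRM, rho 0.3 | MMRM, rho 0.7 | Single-visit ANCOVA |
|---|---|---|---|---|
| 15% | 0.480 | 1.10 | 1.17 | 1.22 |
| 10% | 0.889 | 1.17 | 1.29 | 1.37 |
| 5% | 2.132 | 1.37 | 1.61 | 1.77 |

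**Check by explicit fit.** A generalized least squares fit of the Appendix 1 mean model (750 per arm, SD 20) gave these results at 15% non-users and rho = 0.5: arm-mean SE 0.827 at 50:50 against 0.730 at observed margins, ratio 1.13. At rho = 0.7 the ratio was 1.17. At 5% non-users the ratios were 1.49 (rho = 0.5) and 1.60 (rho = 0.7). The treatment difference and its SE (1.033) were identical under both weightings in every case.

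**Absolute size.** At SD 20 the 95% half-width at observed margins is 1.96 x 20/sqrt(750) = 1.43. In the MMRM at 50:50 it becomes 1.57 to 1.67 at 15% non-users, 1.68 to 1.85 at 10% and 1.97 to 2.31 at 5%. SD 20 is the documents' value for absolute change in mg/dL; the ratios do not depend on it.

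**Shift in the means.** Each arm mean moves by (0.5 - p) x beta, with beta the non-user minus user coefficient. At p = 0.15 this is 0.35 x beta: 0.7, 1.75 or 3.5 points for an assumed beta of 2, 5 or 10, and zero for beta = 0.

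**Why differences are safe.** With no treatment-by-factor interaction, the term w x beta is the same in both arms and cancels at each visit and in any linear combination of visits.

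**Country models.** SAP 6.4.6.1.1 adds country and treatment-by-country to both co-primary models. There the weights do not cancel. With assumed shares of 80%, 15% and 5% in three regions, equal weighting would multiply the SE of the overall difference by sqrt[(1/0.80 + 1/0.15 + 1/0.05)/9] = 1.76. The SAP gives neither code nor weighting for these models.

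**The case against.** The strongest reply is that no tested result depends on this. The hypotheses in SAP 6.4.6.1 concern differences, and the pooling steps in Appendices 2 and 3 combine only differences between arms. The sentence on intervals in SAP 6.4.6.2 follows the list of other secondary endpoints, where p-values are nominal. The code is labelled as a sample. Equal margins are a standard default, and the interval is valid for a 50:50 population. Descriptive summaries by arm will show values at the enrolled mix in any case.

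Most of this stands, and it fixes the point as minor. It does not remove it: Appendix 1 still promises LS means by treatment and visit, its code requests confidence limits for them, and nothing else in the SAP sets a weighting.

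Three stronger readings are tempting and are not supported:

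- A reader might infer that the treatment effect is biased or its interval too wide. In the main models the weights cancel exactly.
- A reader might apply the single-visit ratios (1.22 at 15%, 1.77 at 5%) to the MMRM. They would hold there only if visits were perfectly correlated. They fit the ANCOVA, and only if it uses the same default, which the SAP does not show.
- A reader might take the arm means as known to be displaced, or treat reported lipid levels as wrong. The documents give no user versus non-user coefficient and no results, and SAP 6.4.7 also lists descriptive statistics for actual lipid values.

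**Conclusion.** The point holds as a small reporting correction. If the Appendix 1 code is run as sketched, each arm's LS mean refers to a 50:50 mix that the trial cannot enroll. Relative to the enrolled mix, MMRM arm-mean SEs are larger by about 1.10 to 1.17 times at 15% non-users, 1.17 to 1.29 at 10% and 1.37 to 1.60 at 5%.

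These ranges rest on assumed visit correlations of 0.3 to 0.7 and an assumed non-user share. The documents give only the ceiling of about 15%, which holds whether `statiny` codes statin use alone or any lipid therapy. The shift in the means rests further on an unknown coefficient; the extra width does not. If no subject is a non-user, neither arises, although SAP Table 3 does list a subgroup without lipid therapy. Treatment differences, p-values, testing order and power in the main models are unaffected. The country models are a secondary matter: their weighting is simply not stated.

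**What to change.** Add `OM` to the LSMEANS statement in SAP Appendix 1, without `BYLEVEL` so that both arms share the same weights. Name the margin dataset, for example all randomized subjects, so that the weights do not vary with missing visits. State in SAP 6.4.6.1 that any arm LS means reported from the ANCOVA of the first co-primary endpoint use the same weighting. If equal weights are intended, say so in the SAP and in table footnotes.

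For the treatment-by-country models in SAP 6.4.6.1.1, add a sentence that the overall difference is weighted by observed country or region shares.

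The cost is one SAS option and two or three sentences. No treatment difference in the main models changes.
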